12.2. Reporting of Adverse Events and Device Deficiency

Adverse Events will be recorded and reported according to local regulatory requirements and are outlined in Table 13. It is the responsibility of the Investigator to abide by the adverse event reporting requirements stipulated by local law and the sites' Ethics Committee. Investigators are required to evaluate and document all AEs and Device Deficiencies (per the definitions in Table 12) observed in study subjects from the time they enrolled(signed the ICF) until they are no longer participating in the study. AEs should be followed until one of these criteria is met:

- Until the AE resolves
- Until no further action can be taken for an ongoing AE
- Until the subject exits the trial, or
- Until trial closure

NOTE: In the case of permanent impairment, continue to follow the event until it stabilizes and the overall clinical outcome has been ascertained.

For emergency contact regarding a UADE, SAE and/or SADE, contact a clinical study representative immediately (refer to the study contact list provided in the site's study documents binder/investigator site file or refer to the contact information provided on the title page).

Table 13: Adverse Event Reports

For the following events, reporting requirements are:
 
• Serious Adverse Events (SAE)

Investigators shall immediately adopt appropriate therapeutic measures for subjects, and simultaneously report to the management department of medical device clinical trials in clinical trial institutions in written form. Management department of medical device clinical trials shall report to

Confidential

Medtronic	Immediately
local food and drug regulatory authority and health and family planning competent authority of the province, autonomous region and municipality directly under the central government where the clinical trial institution locates	Within 24 hours
Ethics Committee	Within 24 hours
For the following events, reporting requirements are:	

 All other AEs All other Device Deficiencies 	
Investigators shall record all the adverse events and device deficiencies occurred during the clinical trials. Investigators shall analyze the reasons for the events with the sponsor and document the analysis result in written report, including the comments of continuing, suspending or terminating trials, which shall be reported to the Ethics Committee through management department of medical device clinical trials in clinical trial institutions for review	
Medtronic	Submit in a timely manner after the investigator first learns of the event.
Ethics Committee	Per EC's requirements
For the following events, reporting requirements are:	

 Serious Adverse Events (SAE) DD with SAE potential 	
Sponsor submits to:	
The food and drug regulatory authorities and health and family planning competent authorities at the same level filed	Within 5 working days upon being informed
Other clinical trial institutions and investigators participating in the trial	Within 5 working days upon being informed
Ethics Committee	Timely report to Ethics Committee of the clinical trial institution through management department of medical device clinical trials

Confidential

12.3. Documentation and Reporting of Device Deficiencies

Device Deficiency information will be collected throughout the study and reported to Medtronic. Device Deficiencies that led to an AE are reported on the AE eCRF. Device Deficiencies that did not lead to an AE should be reported on a Device Deficiency eCRF (one for each Device Deficiency).

All Device Deficiencies, regardless if it led to an AE, must be reported. Information reported on the Device Deficiency Form shall include a description of the deficiency, the date of onset, actions taken as a result of the deficiency, the outcome of the event, and the date the deficiency was first noticed by the investigator.

Device deficiencies that did not lead to an adverse event but might have led to an SAE if a) a suitable action had not been taken, or b) an intervention had not been made, or c) circumstances had been less fortunate, should be reported to Medtronic as soon as possible. Initial reporting may be done by phone, fax, e-mail, or on the eCRF completing as much information as is available. The original fully completed Device Deficiency eCRF must be submitted to Medtronic as soon as possible.

Initial reporting of AE/DD may be done by phone, fax, e-mail, or on the eCRF completing as much information as is available. The original fully completed AE eCRF must be submitted to Medtronic as soon as possible. Investigators should contact their Medtronic clinical research specialist or site monitor if they have any questions regarding reportable AE/DD. Medtronic will provide and maintain a listing of current contact details for each site.

13. Data Review Committees

13.1. Clinical Events Committee (CEC) Review

As requested by the sponsor, an independent CEC will review and adjudicate at a minimum all procedure, system, and MRI related adverse events and deaths.

The CEC will consist at least 3 non-Medtronic employed physicians that are not participating investigators for the China Micra™ Transcatheter Pacing Study, including a CEC chairperson. At least three CEC members must adjudicate, at a minimum, all deaths and SAEs related to any component of the system under investigation.

For adverse events and deaths reviewed by the CEC, Medtronic will provide the CEC with the Investigator's description and classification. The CEC is responsible for reviewing the Investigator's assessment and supportive documentation (when available), reviewing applicable definitions, and determining final classifications for all adjudication parameters.

If the CEC disagrees with the investigator's classification of the event, the rationale will be provided to the investigator. If the investigator agrees with the CEC's adjudication, the case report form documenting the AE will be updated accordingly.

If the investigator does not agree with the CEC's adjudication classification, both determinations will be provided within the final report; however the CEC's adjudication will be used for data analysis. The disagreement will also be included in reporting to ethic committees and regulatory authorities, if required.

Confidential

14. Statistical Design and Methods

14.1. Primary Objective

To demonstrate the MICRA TPS is safe by estimating the MICRA TPS implant procedure and/or system related major complications free survival probability through 6 month post implant.

14.1.1. Statistical Design, Methods and Analysis Procedures

14.1.1.1. Hypothesis

The primary endpoint is Micra system and/or procedure related major complications through 6 months post implant. The corresponding statistical hypothesis for this study (utilizing single arm OPC design) is:

$$\begin{aligned} H_0 : S_T &\leq S_0, \\ H_1 : S_T &> S_0 \end{aligned}$$

Where S_T is the expected value of the probability of a subject free from Micra system and/or procedure related major complications through 6 months post implant; S_0 is the OPC. The objective will be considered met if the lower bound of the two-sided 95% confidence interval lower bound for the estimate is greater than 83%.

14.1.1.2. Statistical Analysis Method

- Baseline Patient Demographics

Summary Statistics will be obtained: frequency and percentage will be reported for categorical data; mean, standard deviation, minimum, maximum, median, the 1st and 3rd quartiles will be reported.

- Analysis of the Primary Objective:

All subjects who undergoes an Micra implant procedure will be included in the analysis. The Kaplan-Meier survival analysis will be used to estimate the probability of a subject free from Micra system and/or procedure related major complications. The log-log transformation will be used to calculate the confidence limits.

Definitions:

- Endpoint event for the survival analysis is Micra system and/or procedure related major complications (see 6.2.1)
 - The CEC will finally determine if the adverse event is related to Micra system and/or procedure; and if the adverse event is a major complication
- Censoring occurs in subjects who does not experience any Micra system and/or procedure related major complications
- Follow-up time: from the date of Micra implant procedure to
 - the onset date of a Micra system and/or procedure related major complication, or

Confidential

- study termination date (e.g. subject exit, die, or study closure, etc.), or
- the date of Micra deactivation due to any reason that is not related to the Micra system or procedure (e.g. device system upgrade, the subject's other comorbidities, etc) , or
- the last follow-up date, if none of the above occurs.

- **Analyses of the Secondary Objectives**

The secondary objectives will be analyzed using descriptive statistics. The Statistical Analysis Plan will provide additional details.

- **Safety Evaluation**

All information associated with each adverse event, including event description, severity, and relatedness to the system, etc., will be reported. In addition, event rate will be summarized. The 2-sided 95% Confidence Intervals will be calculated using the Exact Binomial method.

- The statistical analysis of the primary objective will be 2-sided, using 0.05 significance level. The statistical analysis software package SAS will be used to conduct these analysis.

14.1.1.3. Statistical Analysis Procedures

The statistical analysis will follow the requirements documented in the ICH E9, as well as the relevant requirements in the Biostatistic Guidelines for Clinical Trials issued by the Chinese Food and Drug Administration (CFDA). At the same time, all statistical analysis procedures will strictly comply to the standard operating procedures (SOP) of the Medical Research & Biometric Center, National Center for Cardiovascular Diseases.

14.1.2. Sample Size Calculation

14.1.2.1. Total Enrollment Size

The study will require an enrollment size of 82. The study size is calculated based on statistical hypothesis, assumed expected performance, and projected attrition.

14.1.2.2. Rationale and Considerations for Sample Size Determination

The study size is determined by the sample size required for the primary objective. It is reported in the NEJM J2015⁷ that the Micra system and/or procedure related complication free survival probability through 6 months was 96%, (95% CI: 93.3%, 97.6%) in those who underwent Micra system implant

⁷Dwight Reynolds, Gabor Z. Duray , etc..A Leadless Intracardiac TranscatheterPacing System. N Engl JMed 2015;NEJMoa1511643:1-9.

Confidential

procedures. Therefore, we conservatively assume that the expected performance (or, "Success Rate" in later text) in the study population will be 94%. The OPC is set as 83% (the same performance threshold in the FDA approved global study). The sample size calculation assumes the statistical analysis will be carried out on 0.05 significance level, 2-sided, 80% power and 10% study attrition. The minimum sample size requirement is 82. The sample size formula is displayed as following:

$$n = \frac{[Z_{1-\alpha/2} \sqrt{p_0(1-p_0)} + Z_{1-\beta} \sqrt{p_T(1-p_T)}]^2}{(p_T - p_0)^2};$$

Where p_T is the expected success rate, p_0 is the OPC value, Z value is under normal distribution, α is the type I error (or significance level, 0.05 is used) and β is the type II error (0.2 is used to ensure 80% power).

The sample size calculation employed a formula based on the binomial distribution of the asymptotic normality method because the success rate estimate given by the Kaplan-Meier method is consistent with the actual observed success rate if there is no drop-outs.

14.1.2.3. Sample Size Requirement for Each Study Center

The study will be conducted concurrently in multiple clinical study sites. In principle, the number of enrollment at study sites will be evenly distributed to ensure adequate representativeness of each site. The actual number per center may fluctuate based on actual progress. The study will try to ensure the enrollment size at each center is relative balanced, and for a particular center, the maximum enrollment number should not exceed 50% of the total study size.

14.1.3. Significant Level and Statistical Power

For this study, the statistical significance level is set at 0.05 (two-sided), and the statistical power is specified at 80%.

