9.2. Subject Enrollment

- Ethics Committee approval of the China Micra™ Transcatheter Pacing Study Clinical Investigation Plan and Informed Consent Form must be obtained prior to enrolling patients in the study.
- Subjects are considered enrolled in the study upon signing the informed consent and meet all of the inclusion and none of the exclusion criteria. Informed consent must be obtained prior to performing any study-related procedures. Subjects will be assessed to ensure that they meet all of the inclusion and none of the exclusion criteria

Confidential

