14.1.4. Projected Attrition

The study attrition will include all scenarios that result in enrolled subject not being included in the analysis. The common reasons are due to serious protocol deviations (if affects performance evaluation). Other scenarios may include: Micra implant was not carried out or not successful, follow-up visit not completed per study requirement, or subject withdrawal of consent due to other comorbidities, etc. All these scenarios may constitute subject drop-outs. At the same time, it is assumed that follow-up compliance will be high in pacemaker population. The study attrition is assumed to be 10%

Confidential

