6.1 Total Enrollment Size

The study will require an enrollment size of 82. The study size is calculated based on statistical hypothesis, assumed expected performance, and projected attrition.

The study pass/fail criteria are based on statistical hypothesis and final analysis results. The analysis of study primary objective will be 6-month success rate comparing to the pre-specified OPC. If the 95% 2-sided confidence interval (CI) lower bound for the probability of freedom from Micra TPS and/or procedure related major complication is greater than 83%, the study will be considered yielding a positive result, demonstrating the success rate is higher than expected values, i.e. study objective will be met.

The study attrition will include all scenarios that result in enrolled subject not being included in the analysis. The common reasons are due to serious protocol deviations (if it affects performance evaluation). Other scenarios may include: Micra implant was not carried out or not successful, follow-up visit not completed per study requirement, or subject withdrawal of consent due to other comorbidities, etc. All these scenarios may constitute subject drop-outs. At the same time, it is assumed that follow-up compliance will be high in pacemaker population. The study attrition is assumed to be 10%.

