6.2 Rationale and Considerations for Sample Size Determination

The study size is determined by the sample size required for the primary objective. Reynolds et al. reported that the Micra TPS and/or procedure related complication free survival probability through 6 months was 96%, (95% CI: 93.3%, 97.6%) in those who underwent Micra TPS implant procedures.³ Therefore, we conservatively assume that the expected performance (or, "Success Rate" in later text) in the study population will be 94%. The OPC is set as 83% (the same performance threshold in the FDA approved global study). The sample size calculation assumes the statistical analysis will be carried out on 0.05 significance level, 2-sided, 80% power and 10% study attrition. The minimum sample size requirement is 82. The sample size formula is displayed as following:

$$n = \frac{[Z_{1-\alpha/2} \sqrt{p_0(1-p_0)} + Z_{1-\beta} \sqrt{p_T(1-p_T)}]^2}{(p_T - p_0)^2};$$

Where p_T is the expected success rate, p_0 is the OPC value, Z value is under normal distribution, α is the type I error (or significance level, 0.05 is used) and β is the type II error (0.2 is used to ensure 80% power).

The sample size calculation employed a formula based on the binomial distribution of the asymptotic normality method because the success rate estimate given by the Kaplan-Meier method is consistent with the actual observed success rate if there are no drop-outs.

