7.1.3 Analysis Sets

The analysis sets for this study are defined as follows. Further detail regarding the analysis sets can be found in Section 7.1.4.

Full Analysis Set (FAS): This is a dataset defined as Intention-To-Treat principle, it refers to the set of all subjects who participates in the study and is exposed to the investigational device. In the event when primary endpoint data can't be collected from certain subjects, censoring or additional analysis may be applied.

Per Protocol Set (PPS): A subset of study subjects who complies to study protocol (The subject who has a violation related to study inclusion/exclusion criterion will be excluded from the PPS).

Safety Analysis Set (SS): The same definition as FAS should be used. Therefore, no additional definition is provided here.

The primary objective analysis will be performed on the FAS and PPS. The electrical parameters (secondary objective #1) will be analyzed on the FAS and PPS. The safety assessment (secondary objective #2), and all baseline demographic summary will be performed on the FAS. [REDACTED]

[REDACTED] The baseline demographic summary, secondary objectives, [REDACTED] will be performed with available data from the database.

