7.1.4 Pre-specified Protocol Deviations and Flow Chart of Analysis Population Set Determination

The following pre-specified protocol deviation items will be checked according to the principle of statistical analysis by SAS programming. These items may be a little bit different from the protocol deviations reported by clinical operation which are collected by CRF.

(1) Withdrawal of informed consent: Subjects obtain registration number, but do not end up using the study device. These are subjects who have had no exposure to the study device (i.e., no Successful or Unsuccessful Implant form is completed).

(2) Violation of inclusion and exclusion criteria: Subjects do not meet the inclusion criteria set in the protocol or meet the exclusion criteria set in the protocol, and this protocol deviation may severely affect the results of primary endpoint. Whether protocol deviation severely affect the results of primary effective endpoints shall be judged together by sponsor, investigators and statistician through discussion at a final data review meeting prior to final database lock.

(3) Lost to follow-up : Subjects are unable to obtain the primary endpoint (i.e. the primary endpoint is identified as true missing). If a subject has a primary endpoint failure, and later is lost to follow-up (prior to 183 days), the subject will still be included in the primary endpoint analysis. This criterion will only be used for the primary endpoint.

(4) Out of time window: The difference between the 6-month follow-up date after operation and operation date of subjects is less than 183 days and this may severely affect the results of primary endpoint. Whether protocol deviation severely affects the results of primary endpoint will be judged together by sponsor, investigators and statistician by discussion at the final data review meeting prior to final database lock. If a subject has a primary endpoint failure, and later has the 6 month visit too early (prior to 183 days), the subject will still be included in the primary endpoint analysis.

(5) Application of Non-study devices: The device implanted for subject is not the study device specified in study protocol or the subject ended up receiving no device at all. If a subject has a primary endpoint failure during the unsuccessful implant attempt, the subject will still be included in the primary endpoint analysis.

[figure not shown]
FAS= Number of the enrolled patients – Number of patients who withdraw informed consent;

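### The stated 80% power is the target of a normal-approximation formula. The log-log Kaplan-Meier rule that decides the primary objective has 77.9% power at a true 94% with 82 uncensored attempts, and the attrition text does not match the analysis sets.

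*Protocol*

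**What the plan says.** **Sizing.** Protocol 14.1.2.2 and SAP 6.2 assume a true rate of 94% against a performance criterion of 83%, and the Protocol sums up the rest as "2-sided, 80% power and 10% study attrition. The minimum sample size requirement is 82". Both print a one-sample normal-approximation formula. They justify it on the ground that "the success rate estimate given by the Kaplan-Meier method is consistent with the actual observed success rate if there are no drop-outs" (SAP 6.2; the Protocol says the same). Protocol 14.1.3 then gives the power for the study: "For this study, the statistical significance level is set at 0.05 (two-sided), and the statistical power is specified at 80" per cent.

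**Decision.** Protocol 14.1.1.1, 14.1.1.2 and 14.1.5 and SAP 7.9.1.1–7.9.1.2 declare success if the lower two-sided 95% Kaplan-Meier limit, computed on the log-log scale, is above 83%.

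**Who counts.** The 82 are enrolled subjects: "Subjects are considered enrolled in the study upon signing the informed consent and meet all of the inclusion and none of the exclusion criteria" (Protocol 9.2). On attrition, Protocol 14.1.4 says "The study attrition will include all scenarios that result in enrolled subject not being included in the analysis", and the examples in SAP 6.1 include "Micra implant was not carried out or not successful, follow-up visit not completed per study requirement". SAP 7.9.1.2–7.9.1.3 instead puts every attempted implant into the primary analysis on the full analysis set (FAS) and censors early exits. SAP 7.1.4 removes from the FAS only those who withdrew before using the device: "These are subjects who have had no exposure to the study device (i.e., no Successful or Unsuccessful Implant form is completed". On the analysis sets, SAP 7.1.3 adds "The primary objective analysis will be performed on the FAS and PPS", whereas Protocol 14.1.9 assigns the primary objective to the FAS alone.

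**The concern.** A reader takes 80% as the chance of meeting the primary objective if the sponsor's own planning value of 94% is true. That is correct only if the formula describes the test that decides. The reason given for using the formula concerns the point estimate: without drop-outs, Kaplan-Meier equals the observed proportion. The decision rests on the lower limit, and the log-log limit is not the limit implied by the formula.

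The second question is which subjects the 10% allowance removes. With about 80 subjects and 5 to 7 permitted failures, a single subject more or fewer can shift power by several points. The text should therefore be clear about who leaves which analysis set.

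What is at stake is the risk of missing the objective with a device that performs as assumed. A false pass is not the issue.

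**Working it through.** **1. The plan's own figure.** Inputs from Protocol 14.1.2.2: p_T = 0.94, p_0 = 0.83, two-sided alpha 0.05, power 80%, attrition 10%.

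n = [1.96·√(0.83·0.17) + 0.8416·√(0.94·0.06)]² / 0.11² = (0.7362 + 0.1999)² / 0.0121 = 72.42, so 73.
73 / 0.90 = 81.1, so 82. The figure is reproduced. The formula's own power at 73 is 80.4%.

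**2. The deciding rule without censoring.** With d failures in n, S = 1 − d/n and Greenwood's variance is S(1 − S)/n. The lower limit is

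L = S^exp(1.96·se), with se = √(S(1 − S)/n) / (S·|ln S|).

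| n | d | S | se | L | Result |
|---|---|---|---|---|---|
| 82 | 6 | 0.9268 | 0.4083 | 0.8444 | pass |
| 82 | 7 | 0.9146 | 0.3781 | 0.8293 | fail |
| 73 | 5 | 0.9315 | 0.4473 | 0.8432 | pass |
| 73 | 6 | 0.9178 | 0.4084 | 0.8262 | fail |

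The z formula in SAP 7.9.1.2 gives the same boundaries against one-sided 0.025: p = 0.0140 for 6/82, 0.0257 for 7/82, 0.0154 for 5/73 and 0.0287 for 6/73. With zero failures the log-log limit is undefined. I count that as a pass; its probability at 82 is 0.94^82 = 0.6%.

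**3. Exact power and type I error** (binomial probability of at most the permitted number of failures).

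| n | Most failures that pass | True 94% | True 96% | One-sided error at 83% |
|---|---|---|---|---|
| 73 | 5 | 72.7% | 92.8% | 0.99% |
| 74 | 5 | 71.6% | 92.4% | 0.88% |
| 75 | 6 | 83.7% | 97.0% | 2.04% |
| 79 | 6 | 80.5% | 96.1% | 1.30% |
| 80 | 6 | 79.6% | 95.9% | 1.16% |
| 82 | 6 | 77.9% | 95.4% | 0.92% |
| 83 | 7 | 87.5% | 98.2% | 2.02% |

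At 82, a true rate of 94.18% would give 80%.

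**4. Is this only discreteness?** Not entirely. The test implied by the formula is z = (S − 0.83)/√(0.83·0.17/n) > 1.96. It passes 7/82 (z = 2.04) and 6/73 (z = 2.00), with exact power 88.1% and 85.2%. The log-log rule rejects both. At each planning size the sizing test and the deciding test differ by one failure.

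**5. Loss from 82, true 94%.** The documents give no loss mechanism, so these are my assumptions.
- Random removal before any attempt, exact power averaged over the number left: 80.7% at 5%, 77.2% at 10%.
- Simulated censoring (100,000 runs per scenario; dropout uniform over days 1–183; 0, 40 or 80% of events on day 0): 78.4–79.9% at 5% loss, 78.5–80.6% at 10%.
- All dropouts simulated as censored at day 0 before any event: 80.8% at 5%, 77.3% at 10%.

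**6. Attrition against the analysis sets.**

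| Reason in Protocol 14.1.4 / SAP 6.1 | FAS primary analysis | Per-protocol set (PPS), SAP 7.1.4 |
|---|---|---|
| Implant not carried out | out, if no device exposure | out |
| Implant unsuccessful | in (day 0, or the event day) | excluded as no study device |
| Follow-up incomplete or withdrawal after implant | in, censored | excluded if lost without an endpoint, or if the visit was early and judged severe |
| Serious protocol deviation | in | excluded |

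For the last three categories in SAP 7.1.4 (loss to follow-up, out of window, no study device), a subject with a primary endpoint failure stays in the primary endpoint analysis.

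**The case against.** The strongest reply is that nothing has been miscalculated. The formula is printed and named as asymptotic, 80% is openly a design input, and exact binomial power seldom equals a nominal target. This stands as far as the arithmetic goes. It does not make 80% the power of the planned rule, which is how a section on statistical power will be read.

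The gap for the primary analysis is also small. At 82 it turns on 7 failures giving a limit of 82.93%, just under 83%. Power is above 80% at 75 to 79 subjects, and the loss scenarios straddle 80%. The 94% was set deliberately below the 96% reported from the global study. All of this stands and limits the weight of the point.

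A reader might infer from the 73 evaluable subjects that the real power is 72.7%, a shortfall of more than 7 points. The documents do not support that. The FAS keeps every attempted implant and censors early exits, so 73 is not its expected size. Reaching 72.7% needs exactly 9 of 82 never to enter the analysis and no censoring in the rest. Nor is it a forecast for the PPS, whose size and censoring are unknown.

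On attrition, one can say that an unsuccessful attempt without an event is included only formally, since SAP 7.9.1.2 gives it zero follow-up, and that early exits lose information. Allowing for both when inflating the sample is reasonable. The wording is still at odds with the FAS definition.

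**Conclusion.** The point holds, with minor to moderate weight. The sample size is correctly computed, but the 80% belongs to the formula. Under the visible deciding rule, exact power at a true 94% is 77.9% with 82 uncensored attempts, so the chance of missing the objective is 22.1% against the stated 20%. With up to 10% loss it is roughly 77–81%; that range depends on the dropout and event-timing assumptions stated above. The 72.7% at 73 is one point on the sawtooth.

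A reader might also infer that the trial is too small or the test invalid. Neither follows: one-sided type I error is 0.9% at 82, and power at a true 96% is 95.4%.

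The attrition text does conflict with the FAS primary analysis. Most of the reasons it lists are PPS exclusions.

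All power figures use the visible rule. Text after the confidence-interval sentence in SAP 7.9.1.2 is redacted and could add detail.

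**What to change.** Keep 82 subjects, the interval, the p-value and the pass rule.

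1. **Protocol 14.1.2.2–14.1.3 and SAP 6.2 and 6.4.** State: *The 80% is the target power of the normal-approximation formula. Under the planned rule (lower two-sided 95% log-log Kaplan-Meier limit above 83%), exact power at a true 94% is 77.9% with 82 attempted implants and no censoring, and it varies with the number analysed.* If 72.7% at 73 is given at all, label it as one point on that range. Label any range with censoring as simulated and give its assumptions.

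2. **Protocol 14.1.4 and SAP 6.1.** State: *In the FAS primary analysis, only enrolled subjects without device exposure are left out. Attempted implants, successful or not, stay in, and early exits are censored.*

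3. **SAP only**, because the Protocol runs the primary objective on the FAS alone. Add: *Eligibility violations, loss to follow-up, out-of-window visits and no study device lead to exclusion from the PPS as defined in 7.1.4, with the exceptions given there: subjects with a primary endpoint failure are still counted in the primary endpoint analysis.*

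The cost is a few sentences in each document and a slightly less favourable stated power. No further patients are needed and the test does not change.
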